- 1) To compare adherence among persons across the three study arms.
- 2) To evaluate the safety, tolerability and acceptability of treatment in the three arms.

3. Background

Globally, an estimated 70 – 80 million persons are chronically infected with hepatitis C (HCV). Chronic hepatitis C is associated with long-term complications including liver cirrhosis, hepatocellular carcinoma and end-stage liver disease. Chronic hepatitis C is treatable and treatment can cure infection such that HCV RNA is undetectable and persons cannot transmit virus and risk for chronic complications decreases substantially. Treatment access has been hampered in much of the world in part due to the low efficacy and toxicity of the previous generation of regimens. The landscape of HCV treatment has changed dramatically over the past few years with the FDA approval of highly efficacious, non-toxic second generation direct acting antiviral agents. With these advances in treatment, questions have arisen about delivery of these agents among populations in resource-limited settings (RLS) given some of the inherent differences in HCV infected patients in these settings. Ideally, a treatment regimen for RLS should be pan-genotypic; thereby, not requiring HCV genotype testing which can be cost prohibitive and rarely available in these settings. Moreover, treatment delivery strategies need to optimize adherence particularly in populations that have had suboptimal adherence such as people who inject drugs (PWID).

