We recently completed a pilot trial comparing directly the two first available pan-genotypic regimens in India (SOF+PR for 12 weeks and SOF+R for 24 weeks). We used a field-based directly observed therapy (DOT) delivery strategy. While interferon injections for the SOF+PR arm were delivered once weekly in a clinic, all doses of sofosbuvir and ribavirin were dosed in the field by a field worker at a location chosen daily by the participant. Among 50 persons randomized, 88% completed treatment in both arms. However, sustained virologic response at 12 weeks (SVR12) was significantly higher in the SOF+PR arm compared to the SOF+R arm (88% vs 60%). Moreover, no participants in the SOF+PR arm who completed treatment failed therapy. This was despite ongoing substance use in 52% and a median of 2 (Range: 0 -18) missed doses in those who completed therapy in the SOF+PR arm. By contrast, in the SOF+R arm, SVR12 was significantly lower among persons who were actively using drugs or alcohol and who missed >5% of doses. Notably, no serious adverse events occurred in the SOF+PR arm and no one discontinued therapy in the SOF+PR arm due to side effects. While our trial suggested that field-based DOT was feasible in general, there were logistical challenges that we encountered raising questions about whether this is the optimal strategy for all clients. Further, as all patients received DOT the role of DOT itself could not be evaluated. Moreover, since this trial was completed, new generic direct acting antivirals (DAAs) have become available in India and new data have emerged on the efficacy of shorter duration regimens that include 2 DAAs and pegylated interferon. In the 4WIDUC study conducted among PWID in Amsterdam, a 4-week regimen of SOF+ ledipasvir+ pegylated interferon+ ribavirin was associated with an SVR of 94%. Of note, 15/16 patients randomized to this arm completed treatment and all achieved SVR – one patient was lost to follow-up. All patients were on opioid agonist therapy and the comparator arm was another experimental arm and not per guidelines.

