Subjects in Arm 1 will be required to visit the Bilaspur ICC once weekly for four weeks. During these visits, participants in Arm 1 will receive their pegylated interferon alfa-2a shots subcutaneously at the clinic by a registered medical practitioner. They will be compensated INR 100 (USD 1.5) for these visits (since this is not the standard of care).

Subjects in Arms 1 and 2 will also receive 3 doses of SOF and DAC, which they will be instructed to take home and use as backup in case there is a problem receiving the daily medication from field workers. Otherwise, all doses of SOF and DAC will be delivered as directly observed therapy (DOT) daily in the field including Saturday and Sunday doses. Peer-health workers (PHW) (1 per 15-20 participants: total 4 for the study) will deliver the SOF and DAC via DOT on a daily basis to a location of the participant's choosing. We will provide the PHW with laptops/tablets that have a fingerprint reader to record the daily delivery of SOF and DAC and also to also ensure that the drugs are being delivered to the correct participant.

Subjects in Arm 3 will receive their first 4 weeks of treatment supply at baseline and two refills of 28 day's worth of doses at Weeks 4 and 8.

Dose Reduction

If a serious adverse reaction develops in Arm 1 participants during the course of treatment (See Section 8c), the dose of PEG will be modified according to standard guidelines until the AE abates or decreases in severity. See Table 1 for procedures related to depression and see Table 2 for procedures related to hematologic abnormalities. Selective serotonin reuptake inhibitors are available through government hospitals in India and will be made available to study subjects as needed. If persistent or recurrent serious adverse events develop despite adequate dosage adjustment, treatment will be discontinued.

Table 1. Procedures for Dose modification for serious adverse events related to depression

Depression Severity	Initial Management (4-8 weeks)		Depression		
	Dose modification	Visit Schedule	Remains stable	Improves	Worsens
Mild	No change	Evaluate once weekly by clinician at visit and daily recording of symptoms by outreach worker in field	Continue weekly visit schedule	Continue weekly visit schedule	(See moderate or severe depression)

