Moderate	Decrease PEG dose 50%	Evaluate once weekly by clinician at visit and daily recording of symptoms by outreach worker in field	Consider psychiatric consultation. Continue reduced dosing.	If symptoms improve and are stable for 4 weeks, may resume normal visit schedule. Continue reduced dosing or return to normal dose.	(See severe depression)
Severe	Discontinue PEG permanently	Immediate psychiatric consult with CIMS	Psychiatric therapy as necessary as supervised by physician at CIMS		

Table 2. Procedures for Dose modification for serious adverse events related to hematologic abnormalities

Laboratory values		Pegylated Interferon $\alpha 2a$
Hgb	<10.0 g/ dl	---
	<8.5 g/dl	Permanently discontinue
WBC	<1.5 x 10 ⁹ /L	Reduce dose by 50%
	<1.0 x 10 ⁹ /L	Permanently discontinue
Neutrophil	<0.75 x 10 ⁹ /L	Reduce dose by 50%
	<0.5 x 10 ⁹ /L	Permanently discontinue
Platelets	<50 x 10 ⁹ /L	Reduce dose by 50%
	<25 x 10 ⁹ /L	Permanently discontinue
Bilirubin – direct	2.5 x ULN*	Permanently discontinue
Bilirubin – indirect	>5 mg/dl	
	>4 mg/dl (for 4 weeks)	Permanently discontinue
Creatinine	> 2 mg/dl	Permanently discontinue
ALT/AST	2 x baseline and 10 x ULN	Permanently discontinue

*ULN = upper limit of normal

Treatment interruption

We will track missed doses using our biometric system in Arms 1 and 2. Participants who miss ≥ 1 but fewer than 2 weeks of doses will have their treatment extended so that they complete the total number of doses in their assigned arm (e.g., 28 for Arm 1 and 84 for Arm 2). If a client misses 2 weeks or more of therapy,

treatment will be restarted in its entirety at the discretion of the study physician and in consultation with the participant. Treatment can only be restarted one time. If there is a second interruption of >2 weeks, treatment will not be restarted. Participants in Arm 3 will be counseled to complete all doses of medications even if it takes longer than 84 days (e.g., 94 days). If participants in Arm 3 report an interruption >2 weeks at their 4-weekly medication refill visit, they will also be provided with one opportunity to restart treatment for the entire duration of 12 weeks at the discretion of the study clinician as with Arms 1 and 2.

4a5.3. End of Treatment Visit

The following procedures/assessments will be completed at the End of Treatment Visit

- Obtain vital signs
- Assessment of adverse events and concomitant medications

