- Review medication compliance with subject. Subject should bring any missed doses to this visit.
- Obtain blood samples for sample storage in Table 3
- Brief survey on quality of life and alcohol and drug use
- Perform targeted physical examination
- Chart review of YRG-JHU ICC data to document HIV and antiretroviral therapy status and engagement in opioid substitution therapy (OST)

4a5.4. Early termination visit

Subjects discontinuing treatment prior to completion of the assigned dosing period will be asked to complete an Early Termination visit as described below. In addition, these subjects will be asked to complete the 12-week Post Treatment visit. Subjects with HCV RNA < lower limit of quantification (LLOQ) who permanently discontinue all study drugs for any reason including safety and/or tolerability concerns prior to completion of the assigned dosing period will be followed according to the post-treatment study assessments to determine whether the subject achieves SVR.

The Principal Investigator will be consulted prior to subject discontinuation when medically feasible. Study medication will be discontinued in the follow instances:

- Unacceptable toxicity, as defined in Section 8c of the protocol, or toxicity that, in the judgment of the study clinician and principal investigator, compromises the ability to continue study-specific procedures or is considered to not be in the subject's best interest
- Pregnancy in female participants
- Significant protocol violation including non-compliance with study assessments
- Subject requests to discontinue for any reason

The following procedures will be performed at the early termination visit.

- Perform targeted physical examination
- Obtain vital signs
- Obtain body weight
- Assessment of adverse events and concomitant medications
- Obtain blood samples for:
 - HCV RNA testing
 - Complete blood count
 - Liver function tests
 - Renal function tests
 - These samples will be used to estimate FIB-4 (stage fibrosis)
- Brief survey on quality of life and alcohol and drug use
- Subject should return all extra medication doses at this visit
- Chart review of YRG-JHU ICC data to document HIV and antiretroviral therapy status and engagement in opioid substitution therapy (OST)

4a5.5. 12-week post-treatment visit (Week 16 for Arm 1 and Week 24 for Arms 2 and 3)

The following procedures will be performed at the 12-week post treatment visit.

- Obtain vital signs
- Obtain body weight

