Peglyated-interferon alfa-2a is commercially available as Taspiance by Emcure Pharmaceuticals in India and will be provided in this study as 180 µg/0.5 mL pre-filled syringes. Each syringe is to deliver 0.5 mL of drug product. The formulation, which is subcutaneously administered, contains sodium chloride, polysorbate 80, benzyl alcohol, sodium acetate trihydrate, acetic acid, and water for injection. The solution is colorless to light yellow and the pH is 6.0 ± 0.5.

Packaging and Labeling

The PEG will meet all applicable requirements of Good Manufacturing Practices: Manufacture of

investigational medicinal products (July 2003) and the Drug Controller General India (DCGI).

Storage and Handling

Peglyated-interferon alfa-2a prefilled syringes will be stored in the refrigerator at 2 °C to 8 °C (36 °F to 46 °F) protected from light and will not be frozen or shaken. Syringes are for single use only.

b. Justification and safety information if FDA approved drugs will be administered for non-FDA approved indications or if doses or routes of administration or participant populations are changed.

N/A

c. Justification and safety information if non-FDA approved drugs without an IND will be administered.

N/A

7. Study Statistics

a. Primary outcome variable.

The primary outcome will be sustained virologic response (SVR12), which is defined as HCV RNA < lower limit of quantification 12 weeks after treatment completion.

b. Secondary outcome variables.

Adherence for comparison across the three arms will be defined using a combination of the biometric data for Arms 1 and 2 and self-report and pill counts for Arm 3. Serious adverse events requiring dose modification or treatment discontinuation will include primarily laboratory abnormalities including anemia, neutropenia and thrombocytopenia. For any adverse event outcome, we will consider occurrence of any of the side effects commonly associated with treatment with pegylated interferon alfa-2a, including but not limited to fatigue, headache, pyrexia, myalgia, rigors, insomnia, nausea, alopecia, irritability, arthralgia, anorexia, dermatitis, depression, or fatigue.

c. Statistical plan including sample size justification and interim data analysis.

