All analyses will be conducted as intention to treat. We will use a chi-squared test of proportions to compare the proportions that achieve SVR12. Pairwise comparisons with correction for multiple comparisons will be conducted to directly compare Arms 1 and 2, Arms 1 and 3 and Arms 2 and 3. For secondary outcomes, chi squared tests of proportions will be used to compare categorical outcomes and a Wilcoxon rank-sum test will be used to compare adherence.

The primary objective of this study is to test the feasibility of DOT for HCV treatment among HCV-infected persons with substance use history in a resource limited setting. An additional objective is to generate pilot data to plan a larger powered study. We hypothesize that SVR12 will be higher in Arm 1 compared to Arms 2 and 3. Assuming a two-sided $\alpha=0.05$, 50 people in each arm and 70% achieving SVR12 in Arm 3, we will have >80% power to detect a difference of 25% (e.g., 95% completion in the SOF+DAC+PEG).

No interim analyses will be conducted as with 150 participants, it will not be possible to observe statistical differences prior to the completion of the trial.

d. Early stopping rules.

As we do not plan to do interim analyses, the only reason for stopping the trial would be a higher frequency than expected of serious adverse events. We will continually monitor the frequency of serious adverse events and if this frequency is 10% or higher, we will prematurely stop the trial.

8. Risks

a. Medical risks, listing all procedures, their major and minor risks and expected frequency.

It is anticipated that most participants who complete their full course of treatment with optimal adherence will clear hepatitis C from their bodies. However, for those individuals who do not respond to treatment, it is possible that non-response will affect their ability to respond to other drugs for hepatitis C in the future. However, with the newer direct acting antiviral (DAA) regimens, response rates have been demonstrated to be comparable in treatment naïve and prior non-responders. The primary risk related to taking these medications is with respect to side effects associated with pegylated interferon alfa2a.

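### Adherence comes from fingerprint delivery records in Arms 1 and 2 but from self-report and pill counts in Arm 3, and as written a home backup dose that was taken scores as missed; Arm 3 contrasts therefore mix measurement with delivery method.

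*Combined protocol and SAP*

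**What the plan says.** Secondary objective 1 (Section 2) is: "To compare adherence among persons across the three study arms". Section 7b defines the outcome "using a combination of the biometric data for Arms 1 and 2 and self-report and pill counts for Arm 3", and Section 7c says that "a Wilcoxon rank-sum test will be used to compare adherence". Neither section gives a common measure or a sensitivity analysis for adherence.

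The biometric record is described in Section 4a5.2. Peer-health workers carry a device with a "fingerprint reader to record the daily delivery of SOF and DAC". Under Treatment interruption in the same section: "We will track missed doses using our biometric system in Arms 1 and 2". Participants in Arms 1 and 2 also take home three doses of both oral drugs to "use as backup in case there is a problem receiving the daily medication from field workers".

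Section 4a5.3 (End of Treatment) says, without limiting it to any arm: "Review medication compliance with subject. Subject should bring any missed doses to this visit". Section 4a5.4 asks for surplus doses back at early termination. Table 3 lists an adherence assessment at End of Treatment; its footnote is not in the text supplied, so nothing here rests on it.

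**The concern.** Arm 2 and Arm 3 receive the same drugs for the same 12 weeks and differ in delivery, so this is the contrast that isolates directly observed therapy (DOT). Section 3 says of the earlier pilot that "as all patients received DOT the role of DOT itself could not be evaluated". In this contrast the adherence record changes exactly when the delivery method changes, so a difference, or the absence of one, may come from the record.

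The backup doses make this concrete. They are meant for days without field delivery, while the biometric system logs delivery and supplies the missed-dose count. Section 7b names no other source for Arms 1 and 2. A participant who takes a backup as instructed therefore appears to have missed a dose. An Arm 3 participant who takes a tablet at home has it credited by self-report and pill count.

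At stake are secondary objective 1 and the adherence data that this pilot would hand to a larger trial.

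**Working it through.** **The plan's own figure.** There is none for adherence. The only power statement (7c, above 80% for SVR12 of 70% vs 95%, 50 per arm) reproduces at 92.0%, or 87.1% with continuity correction, and does not bear on this point.

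**Inputs from the protocol.** Three backup doses (4a5.2); planned courses of 28 and 84 doses (4a5.2, Treatment interruption); 50 per arm and two-sided 0.05 (7c, stated there for SVR12); pilot misses with median 2 and range 0–18 among completers of one DOT arm (Sections 1 and 3).

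**Assumptions.** The protocol gives no rate of delivery failure, backup use or misreporting. Daily failure p is set at 0.5%, 1% and 2%. Each failed day uses a backup until three are gone, with none reissued.

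**Upper bound.** Arm 1: 3/28 = 10.7%. Arm 2: 3/84 = 3.6%.

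**Expected shift.** Backups used = E[min(X, 3)], with X ~ Binomial(days, p), which equals P(X≥1) + P(X≥2) + P(X≥3). For Arm 2 at p = 1%: 0.570 + 0.205 + 0.053 = 0.828 doses, and 0.828/84 = 0.99%.

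| p | Arm 1: doses (share of 28) | Arm 2: doses (share of 84) |
|---|---|---|
| 0.5% | 0.140 (0.50%) | 0.419 (0.50%) |
| 1% | 0.280 (1.00%) | 0.828 (0.99%) |
| 2% | 0.558 (1.99%) | 1.556 (1.85%) |

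The two DOT arms shift almost equally (a gap of at most 1.99 − 1.85 = 0.14 points here), so the distortion falls on contrasts with Arm 3.

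**Effect on the planned test.** Simulated rank-sum test, Arm 2 vs Arm 3, 50 per arm, uncorrected two-sided 0.05, equal true misses, with unrecorded Arm 2 backups added as misses. The pilot-like shape is negative binomial with size 0.7 and mean 3.5 (median 2, 98th percentile 17). The wider shapes have size 1.0 and mean 9 (median 6), or size 0.5 and mean 12 (median 5). False rejection rates, to within about a point or two of simulation error:

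| Setting | p = 0.5% | p = 1% | p = 2% |
|---|---|---|---|
| Pilot-like misses, no used backup recorded | 13% | 34% | 76% |
| Pilot-like misses, half of used backups recorded | 7% | 12% | 29% |
| Wider spread, no used backup recorded | 7% | 10% | 24% |
| All used backups counted | 5% | 5% | 5% |

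**Error in the record itself.** With the pilot-like shape and no backup problem, if one arm's record hides 25% or 50% of misses, the test falsely rejects about 15% or 56% of the time. Counting backups does not remove this part.

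**Denominator.** Section 4a5.2 extends treatment after shorter interruptions until 28 or 84 doses are complete, and allows one restart. Someone in Arm 2 who misses 2 days and is extended has 84/84 = 100% by doses completed, or 82/84 = 97.6% by planned days. Section 7b does not say which applies.

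**The case against.** **The figures rest on assumptions.** This stands. The highest row needs every used backup to go unrecorded and gives Arm 3, which has no DOT, the missed-dose pattern of completers in a DOT arm on another regimen. Section 7c also plans corrected pairwise comparisons; whether that reaches adherence is unclear. At 0.05/3 the highest row becomes about 6%, 19% and 60%, against a nominal 1.7%. In points of adherence the backup shift is modest: below 2 points in Arm 2 at these rates, where the only adherence level cited from the pilot is more than 5% of doses missed.

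**Staff would in practice learn of backup use.** The extension rule needs the number of doses taken, and compliance is reviewed in all arms at End of Treatment. The data may well exist, but 7b does not bring them into the outcome for Arms 1 and 2.

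**Different records cannot be avoided.** This is true of daily scans under monthly dispensing. It is not true of the backup rule or of a common end-of-treatment measure.

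**Stronger readings a reader might infer.** One is that the comparison is tilted against DOT. The documents do not support a direction: unrecorded backups lower measured adherence in the DOT arms, unverified backups credited as taken would raise it, and the error in Arm 3 self-report is unknown. Another is that the role of DOT cannot be assessed at all. SVR12 in Arm 2 vs Arm 3 also addresses it and does not use this record. A third is that adverse-event contrasts fail for the same reason. How often participants are asked about symptoms is a separate matter, and this point gives no support for that claim.

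**Conclusion.** The point holds for secondary objective 1 and should be fixed before analysis. As written, adherence in Arm 3 is measured differently from adherence in the DOT arms, and a backup dose taken as instructed counts against the DOT arms. The backup effect cannot exceed 10.7% of the Arm 1 course or 3.6% of the Arm 2 course. At the assumed failure rates it is about 0.5 to 2 points. That can be enough to disturb the Arm 2 vs Arm 3 test when true misses are few and tightly grouped, and less so when they are spread out or when backups are partly recorded. The 76% figure is one corner of an illustration, not an estimate for this trial. The net direction of the whole measurement difference is unknown, some of it will remain under any rule, and SVR12 and its power are unaffected.

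**What to change.** 1. **Section 7b, counting rule.** In Arms 1 and 2, define doses taken as fingerprint-recorded doses plus backups used, where backups used are backups issued (including any reissued) minus unused backups brought to End of Treatment or Early Termination. Add a sensitivity analysis that scores unreturned backups as not taken.
2. **Section 7b, extension and restart.** State one rule, the same in all arms, for how doses taken during an extension or after a restart enter the numerator and the denominator. This concerns scoring only, not when treatment is extended or restarted.
3. **Section 7c, common source.** Add a three-arm sensitivity comparison based on the self-report and leftover-dose review already done at End of Treatment in every arm. Report it beside the main result with 95% confidence intervals, and state that Arm 3 contrasts carry a measurement difference.

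The cost is some wording and a count of a few tablets per DOT participant at visits that already collect leftover doses; no visit is added. The common measure is less precise than fingerprints, so it belongs in a sensitivity analysis and should not replace the biometric record. It shows how far the result depends on the source but does not remove the difference.
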